#### **8.5 Histopathology of Excised LN**

The presence of lymphoid tissue for each excised LN will be confirmed by tissue analysis. All LNs will be routinely sectioned and stained with hematoxylin and eosin (H&E). LN ultra-staging will be performed according to the method of Kim et al. Briefly, two adjacent 5- $\mu$ m sections will be cut and sectioned at each of the two levels, 50- $\mu$ m apart from each paraffin block. Sections at each level will be stained with H&E and with immunohistochemistry using anti-cytokeratin AE1:AE3. Image Acquisition and Transmission

Videos of the image sequences acquired using PINPOINT will be recorded to a medical grade video recorder. All required images will be provided to the Sponsor by the Investigative Center.

Image files will be identified using the subject number and initials only (no information identifying the subject shall be included in the files).

## **9 EVALUATION, RECORDING, AND REPORTING OF ADVERSE EVENTS**

All untoward medical occurrences either observed by the Investigator or one of his/her medical collaborators, or reported by the subject spontaneously, or in response to the direct question below, will be reported as follows:

- All events occurring before randomization should be recorded in the source documents and will be considered part of the subject's case history.
- All adverse events occurring during the study will be recorded as adverse events on the adverse event CRF.
- Events occurring as a result of the surgery will be reported as adverse events related to the surgical procedure in the adverse event CRF.
- Events related to PINPOINT will be recorded as adverse device effects in the CRF.
  - Events that are not related to PINPOINT shall be recorded as adverse events.
- Events related to PINPOINT that affect a user of the device (non-subject) are recorded as technical complaints.
- Events related to IC2000 and/or Blue dye will be recorded as adverse events related to IC2000 and/or blue dye in the adverse event CRF.

In an attempt to optimize consistency of AE reporting across centers, the subjects must be asked a standard question to elicit events. At each clinic or telephone evaluation of the subject, study personnel will ask the following questions: "Have you had any problems since your last visit?"

AEs reported on the CRF will include the date of onset, severity, relationship to PINPOINT, IC2000 and/or Blue dye, relationship to surgical procedure, date of resolution (or the fact that it is ongoing or has become chronic), action taken, and whether the AE is serious or not.

### **9.1 Definitions**

#### **9.1.1 Adverse Event (AE)**

Any untoward medical occurrence, unintended disease or injury or any untoward clinical signs (including an abnormal laboratory findings) in subjects whether or not related to the investigational medical device.

- Includes events related to the IC2000 or Blue dye.
- Includes events related to procedures involved (any procedure in the clinical investigation plan).
- Postoperative nausea or vomiting occurring during the first 24 to 48 hours, and post-operative pain related to surgical procedure is not considered an adverse event.

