## 6.3 Concomitant Treatment

Any concomitant medications the subject is receiving at the start of the study (Day 0) or given for any reason during the study must be recorded in the CRF and source documents with the

exception of routine medications given for preparation of surgery, during surgery and post-operative care. These include but are not limited to the following:

- Sedatives and anesthetics
- Anticoagulants
- Prophylactic antibiotics
- Anti-emetics
- Routine post-operative pain medications

The drug name, start and stop dates, indication, dose, frequency and route information will be recorded for concomitant medications.

Other surgical and diagnostic procedures concomitant to the laparoscopic hysterectomy, trachelectomy, conization and lymphatic mapping procedure that take place during the study must be recorded in the CRF and in the source document, including start and stop dates.

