### **7.2 Indocyanine Green (IC2000)**

IC2000 will be injected directly into the cervical submucosa and stroma; and will not be administered intravenously. Additionally, the subject is anesthetized and the cervix and uterus are removed as part of the surgical procedure. Therefore the risks associated with injection into the cervix are expected to be lower than those associated with intravenous administration. Based on the clinical information for systemic ICG administration, the risks and precautions are discussed below.

Severe allergic reaction (affects fewer than one in every 10,000 subjects) with symptoms that could include the following: tightness in the throat, itchy skin, blotchy skin, rash, coronary artery spasm, facial edema, breathing difficulties, tightness and/or pain in the chest, faster heartbeat, a fall in blood pressure and shortness of breath, cardiac arrest, restlessness, nausea, feeling of warmth, flushes, hypereosinophilia.

The possibility of an allergic reaction is greater in subjects with extremely serious kidney failure. To minimize the risk of an allergic reaction, all subjects with renal dysfunction are excluded as well as subjects with a known allergy to iodine, ICG or iodine dyes.

IC2000 contains sodium iodide and should be used with caution in subjects who have a history of allergy to iodides or iodinated imaging agents. Anaphylactic or urticarial reactions have been reported in subjects with and without history of allergy to iodides. Anaphylactic deaths have been reported following ICG administration during cardiac catheterization.

Radioactive iodine uptake studies should not be performed for at least 1 week following IC2000 administration.

Animal reproduction studies have not been conducted with ICG or IC2000. It is not known whether ICG or IC2000 can cause fetal harm when administered to a pregnant woman or can affect reproduction capacity. It is not known whether ICG or IC 2000 is secreted in human milk. Women who are pregnant or lactating are excluded from this study.

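### The early nausea and vomiting exclusion in Section 9.1.1 has no limit on cause or seriousness and no single window, and it conflicts with the rules that dye-related events are recorded as adverse events

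*Protocol*

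**What the plan says.** Protocol Section 9.1.1 defines an adverse event broadly and then adds three bullets. The first brings the dyes in: "Includes events related to the IC2000 or Blue dye". The third takes something out: "Postoperative nausea or vomiting occurring during the first 24 to 48 hours, and post-operative pain related to surgical procedure is not considered an adverse event". The part at issue is "Postoperative nausea or vomiting occurring during the first 24 to 48 hours".

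The opening of Section 9 has its own recording rule, with no exception for nausea: "Events related to IC2000 and/or Blue dye will be recorded as adverse events related to IC2000 and/or blue dye in the adverse event CRF".

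Other provisions depend on whether an event counts as an adverse event:

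- Section 9.1.3 defines a serious adverse event as an adverse event that meets one of the listed criteria, among them prolonged hospitalization. Section 9.3 requires such events to reach the sponsor within 24 hours of discovery.
- Section 9 asks for relationship to PINPOINT, the dyes and surgery for adverse events entered on the CRF. Section 9.2.2 defines the relationship categories for an adverse event.
- Section 6.3 requires concomitant medications to be recorded, with the "exception of routine medications given for preparation of surgery, during surgery and post-operative care". Anti-emetics are among the examples of that exempt group.

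The SAP, under Safety Outcomes, tabulates adverse events by intensity and relationship and gives each term an exact binomial 95% interval. It neither repeats the exclusion nor resolves it.

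**The concern.** The safety of interstitial ICG is a secondary objective (Section 2.1.2), and the incidence of adverse events is a secondary variable (Protocol Summary). Section 1.2 acknowledges that interstitial IC2000 has not been studied for this use. Every subject is meant to receive both dyes, so there is no dye-free group, and attribution rests on the investigator's judgement of relationship. An exclusion that acts before that judgement is made can bypass it.

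Timing adds to this. Both dyes are injected under anesthesia (Sections 8.3.1.1 and 8.3.1.2), so a subject can first report nausea only after surgery, inside the excluded window. The end of that window is also open. At up to 10 centers, vomiting at 36 hours could be an adverse event at one and not at another, although Section 9 aims for consistent reporting across centers.

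**Working it through.** No power, alpha or sample size figure is involved, so the check is mainly a reading of the provisions together.

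**Step 1: scope of the exclusion.** The sentence in Section 9.1.1 has two items divided by a comma: early nausea or vomiting, and postoperative pain. The phrase tying the event to surgery follows pain only. As punctuated, the nausea item carries no condition on cause, severity or seriousness. A reader could stretch the phrase over both items, but the text does not require it.

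**Step 2: the window.** It is a range. No rule chooses between 24 and 48 hours, and no start point is given.

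**Step 3: early isolated vomiting that the investigator suspects is dye-related.**

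| Provision | Result |
|---|---|
| Section 9.1.1, first bullet | An adverse event |
| Section 9, recording rule for the dyes | Entered on the adverse event CRF |
| Section 9.1.1, third bullet, as punctuated | Not an adverse event |

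No provision ranks these. A coordinator could reasonably let the specific exclusion override the general inclusion. Relationship is collected only for events already treated as adverse events, so an event screened out at that point is never put to the question that would bring it back in.

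**Step 4: consequences of the literal reading.** Serious adverse events are a subset of adverse events. Vomiting in the window that prolongs hospitalization would therefore not be one, and the 24-hour report would not be triggered. If the treatment was a routine anti-emetic, Section 6.3 would not require it on the CRF either.

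**Step 5: illustration of what the SAP would report.** Assume that all 150 planned subjects (Section 4.1) are in the safety set, and use the SAP's exact method.

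- Literal exclusion, 0 of 150: the upper limit is 1 − 0.025^(1/150) = 0.0243, so the report is 0% (0% to 2.4%), whatever the true rate.
- If 3 such events were in fact suspected (assumed): 3/150 = 2.0% (0.4% to 5.7%).
- If 10 were (assumed): 10/150 = 6.7% (3.2% to 11.9%).

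The counts 3 and 10 only show how the reported figure would move. The documents give no rate for early nausea and none for dye-suspected nausea.

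**The case against.** The strongest reply is that two provisions already require dye-related events to be recorded, so the exclusion was meant only for ordinary postoperative nausea. The two items share one predicate, and the reference to surgery can be read as governing both. On that reading nothing dye-related is lost, and the argument about serious events falls with it. This stands as a possible reading, and it is why the defect is an unresolved conflict. It does not settle the matter, because the text does not choose that reading and the open window remains on either one.

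A reader might infer four stronger things that the documents do not support.

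- *That early dye-related reactions as a class are removed by rule.* Only isolated nausea or vomiting is touched. Rash, a fall in blood pressure, breathing difficulty and other signs remain adverse events. Section 8.1 collects events intraoperatively, and an allergic reaction that includes nausea is still recordable as that reaction.
- *That Section 7.2 makes nausea a known stand-alone reaction to this injection.* Nausea is in its list ("cardiac arrest, restlessness, nausea, feeling of warmth, flushes, hypereosinophilia"), but the list belongs to "Severe allergic reaction (affects fewer than one in every 10,000 subjects) with symptoms that could include the following" and the section states its basis: "Based on the clinical information for systemic ICG administration, the risks and precautions are discussed below". It also expects lower risk after cervical injection. At that ceiling, 150 × 1/10,000 = 0.015 such reactions.
- *That the number of lost events can be estimated, or compared with the 2% in Section 7.3.* That figure is for severe anaphylactic reactions to Blue dye, which Section 9.1.1 does not exclude.
- *That the rule favors IC2000.* It applies to both dyes. Both arms are to receive both, and the SAP's Fisher tests compare orders of administration. No efficacy test uses adverse events.

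On concomitant medication, the reply is partly right. Section 6.3 exempts routine use only, Section 9 collects the action taken for recorded events, and source documents (Section 13.2.2) must hold relevant observations. An excluded event could therefore leave no CRF trace, but it need not vanish from the source record.

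**Conclusion.** The point holds as an internal conflict with a practical consequence. Section 9.1.1 excludes early nausea and vomiting without an explicit limit on cause or seriousness and without a fixed window, while its first bullet and the opening of Section 9 require dye-related events to be recorded. If sites follow the exclusion literally, isolated nausea or vomiting that is suspected to be dye-related or is serious goes unrecorded, unassessed for relationship and unreported as serious, and classification between 24 and 48 hours may differ by site.

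The size of any under-count cannot be derived from the documents, and most early nausea may well be routine. The effect is on absolute counts for both dyes, not on the arm comparison or the primary analysis. The change should be made because safety of the interstitial route is a stated objective and the correction is small. The conclusion assumes that no CRF guidance outside these documents already resolves the conflict.

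**What to change.** Reconcile Protocol Sections 6.3, 9, 9.1.1 and 9.1.3:

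- In Section 9.1.1, give one window with a defined start and end. The sponsor should choose its length.
- Limit the exclusion to nausea or vomiting in that window, and surgical pain, that the investigator judges not suspected to be related to IC2000, Blue dye or PINPOINT and that meets no criterion in Section 9.1.3. Everything else is recorded, so relationship and seriousness are considered before an event is set aside.
- In Section 6.3, require anti-emetics to be recorded when given for a recorded adverse event.
- Carry the same wording into the CRF guidance.

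This changes what is recorded, not how subjects are treated, and it keeps the filter on routine postoperative nausea. The cost is two sentences and the guidance, a few more adverse event entries, and a slightly higher reported adverse event rate.

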### 9.1.2 Adverse Device Effect (ADE)

Any adverse event related to the use of PINPOINT (includes all hardware components).

- Includes any event that is a result of a use error or intentional misuse.

ADEs that affect subjects will be recorded as ADEs in the AE CRF. ADEs that only affect a user (non-subject) are recorded in the technical complaint form only.

### 9.1.3 Serious Adverse Event

(SAE) Any adverse event that:

- a. Led to a death.
- b. Led to a serious deterioration in health that either:
  - i. Resulted in a life-threatening illness or injury,
  - ii. Resulted in a permanent impairment of a body structure or a body function,
  - iii. Required in-patient hospitalization or prolongation of existing hospitalization,
  - iv. Resulted in medical or surgical intervention to prevent life threatening illness or injury or permanent impairment to a body structure or a body function.
- c. Led to fetal distress, fetal death or a congenital abnormality or birth defect.

This includes device deficiencies that might have led to a serious adverse event if suitable action had not been taken; intervention had not been made, or if circumstances had been less fortunate. These are handled as SAEs. A planned hospitalization for pre-existing condition, or a procedure required by the protocol, without a serious deterioration in health, is not considered to be a serious adverse event.

### 9.1.4 Unanticipated Adverse Device Effect

(UADE) Any ADE that meets the following:

- By its nature, incidence, severity or outcome has not been identified in the current version of the PINPOINT risk analysis report.
- On health or safety, any life-threatening problem or death caused by, or associated with a device, if that effect, problem, or death was not previously identified in nature, severity, or degree of incidence in the application; or any other unanticipated serious problem associated with a device that relates to the rights, safety, or welfare of subjects.

## 9.2 Adverse Event Descriptions

### 9.2.1 Intensity

The intensity of AEs, including ADEs will be characterized as mild, moderate, or severe, as follows:

Mild	Usually transient, requiring no special treatment, and does not interfere with the subject's daily activities.
Moderate	Introduces a low level of inconvenience or concern to the subject and may interfere with daily activities, but is usually ameliorated by simple therapeutic measures.
Severe	Significantly interferes with a subject's usual daily activities and requires systemic drug therapy or other treatment, if available.

### 9.2.2 Relationship

Suspected	There is a reasonable possibility that the AE is associated with use of the study device or treatment (IC2000 or Blue dye), such as temporal relationship of the event to use.
Not suspected	A relationship between the AE and the study device or treatment (IC2000 or Blue dye) can reasonably be ruled out based on lack of any temporal relationship of the event to use, or when the subject's underlying condition, medical history, or other therapy provide sufficient explanation for the observed event.

## 9.3 Reporting and Evaluation of Serious Adverse Events and Unanticipated Adverse Device Effects

Any SAE or UADE occurring in this study must be reported immediately (within 24 hours of discovery) by email to the Novadaq contact listed below:

### Attention: [name]

[contact] [name]

Email: [[contact]](mailto:[contact])

SAEs and UADEs will be reported to the Institutional Review Board (IRB)/Ethics Committee (EC) according to the institution's policies, but within 10 days of occurrence.

The Sponsor will be responsible for reporting SAEs/UADEs to the FDA or Health Canada in accordance with federal regulatory requirements.

The Sponsor will provide documentation of reportable events to the Investigator, as specified in [Section 13.1.4](#).

The Investigator will ensure that the subject receives appropriate medical treatment and that the subject is followed up until the SAE or UADE resolves or becomes chronic, as defined in [Section 9.4](#).

## 9.4 Follow-up for Adverse Device Effects and Adverse Events

Throughout the study to the final study visit contact, ADEs will be followed until they resolve or become chronic. All AEs will be followed throughout the study until the Day 30 visit. All AEs

related to the PINPOINT, IC2000, Blue dye or the mapping procedures, as determined by the Investigator, will be followed until resolution or deemed chronic

At the final study visit, new AEs, as well as follow-up information for continuing AEs, will be recorded in the CRF and source document. If an SAE or UADE is unresolved at the final study visit, it will be followed by the Investigator until it resolves or becomes chronic (as judged by the Investigator). Follow-up data for such SAEs will be recorded in the source document and reported to the safety contacts. Non-serious ongoing AEs will be followed beyond the final study visit if they are related to the study procedures at the discretion of the Investigator.

## **9.5 Reporting of Technical Complaints/Device Deficiencies**

### **9.5.1 Definitions**

**Device Complaint:** A quality complaint received in writing, electronically, or orally that alleges deficiencies related to the identity, quality, durability, reliability, safety, effectiveness, or performance of a device product. (In this definition, "effectiveness" refers to the actual function of the device, not to how the subject responds to the action of the device. Also in this definition, "device product" refers only to devices provided by the Sponsor for clinical studies and to investigational devices.)

In this definition, safety includes the safety of a subject, user, or other person associated with the use of a medical device.

**Device Deficiency:** Inadequacy of a medical device with respect to its identity, quality, durability, reliability, safety or performance. Device deficiencies include malfunctions, use errors and inadequate labelling.

### **9.5.2 Reporting Procedures**

Any technical complaint/device deficiency should be reported to the Sponsor. Technical Complaints occurring in this study must be reported immediately (within 24 hours) by fax or email to the appropriate Novadaq representative or to Novadaq Quality ([[contact]](mailto:[contact]))

Any complaint about a device must be reported regardless of whether the defect or deficiency had any effect on a subject or on study personnel.

## **9.6 ADEs Technical Complaints/Device Deficiencies that are UADEs**

Novadaq will evaluate all ADE reports and technical complaints/device deficiencies to determine if the report meets the definition of an unanticipated adverse device effect. If Novadaq determines that it does meet the definition, an investigation will be begun immediately. Novadaq will inform the Investigator of any additional reporting requirements beyond those stated in [Sections 9.4](#) and [9.5](#) as applicable.

Novadaq will report the UADE and the results of any investigations to the FDA and Health Canada according to the applicable regulatory guidelines. Novadaq will also report to the Investigator(s), who will submit the required reports to their IRB/ECs within 10 working days after Novadaq first received notice of the effect.

## 10 STATISTICAL CONSIDERATIONS

### 10.1 Primary Objective

To assess the effectiveness of intraoperative PINPOINT in identification of LNs in subjects with uterine and cervical malignancies who are undergoing LN mapping.

### 10.2 Hypotheses

To assess the effectiveness of PINPOINT in the identification of LNs, a non-inferiority test will be performed using the per-protocol (PP) analysis population.

$$\begin{aligned} H_{01}: \quad p_t &\leq p_c - 0.05 \\ H_{11}: \quad p_t &> p_c - 0.05 \end{aligned}$$

Here  $p_t$  and  $p_c$  represent the effectiveness of LN mapping with PINPOINT and Blue dye respectively. We define the numerator for  $p_t$  as the number of nodes identified with PINPOINT (classifications 1, 3, 5, 7 as defined in section 8.3.1.5) and confirmed as lymphoid tissue, and we define the numerator for  $p_c$  as the number of nodes identified with Blue dye (classifications 2, 3, 6, 7 as defined in section 8.3.1.5) and confirmed as lymphoid tissue. We define the denominator for both  $p_t$  and  $p_c$  as the number of nodes identified by ANY method (classifications 1-7 as defined in section 8.3.1.5). The denominator will include excised nodes confirmed as lymphoid tissue.

A non-inferiority margin of 0.05 was determined to be clinically significant based on feedback from Investigators. Within their respective groups,  $p_t$  and  $p_c$  represent the proportion of LNs identified (and confirmed to be lymphoid tissue, See [Section 8.5](#)) with PINPOINT and Blue dye respectively divided by the total number of LNs identified and excised, across all subjects.

We will repeat the analysis described above using the as-treated (AT) analysis set as a supporting analysis of the primary outcome.

As a sensitivity analysis we will also perform the non-inferiority test using the mITT analysis set. We will also perform sensitivity analyses of the primary endpoint using a best-case and a worst-case scenario. The best-case scenario will consider nodes with missing histology to be lymphoid tissue for PINPOINT and non-lymphoid tissue for Blue dye. The worst case scenario will consider nodes with missing histology to be non-lymphoid tissue for PINPOINT and lymphoid tissue for Blue dye.

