***Study Variables:***

**Primary Variables**

Effectiveness of intraoperative PINPOINT and Blue dye in identifying LNs defined as the proportion of LNs identified by PINPOINT and Blue dye respectively (confirmed as lymphoid tissue by histology) divided by the total number of LNs identified and excised.

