#### 10.4 Sample Size Considerations

The clinical literature provides an estimate of the expected effectiveness of LN mapping with ICG and Blue Dye. 12 studies using ICG for the purposes of LN mapping have been published (Table 1). Detection rates for LN mapping with ICG and Blue dye are reported to occur in a wide range (33-100% for ICG and 40-80% for Blue dye). A number of factors play a role in the identification of LN including tumor size, familiarity with LN mapping technique (learning curve) and obesity.

A weighted average of published LN detection rates for Blue dye and ICG (i.e., PINPOINT) in gynecological cancer suggests unilateral detection rates of 91% for ICG and 80% for Blue dye. However, we assumed LN detection rates in gynecological cancer of 84% and 80% using ICG and Blue dye, respectively. We used a lower LN detection rate of 84% for ICG and a LN detection rate at the upper end of the range for Blue dye as a conservative approach to the sample size calculation. We also assumed a non-inferiority margin of 5%.

The power calculation was performed for a 2-level hierarchical model in which nodes are nested within subject. Power was calculated as a function of the effective sample size (ESS), which is a function of the total number of nodes excised, the number of nodes within subjects (clusters), and the intra-cluster correlation (ICC). Specifically,  $ESS = n / VIF$ , where  $n$  is the total number of nodes excised across all patients, and VIF is the variance inflation factor, calculated as

$VIF = 1 + (m - 1) \times ICC$ , where  $m$  is the number of nodes per subject. Because we expect to excise 3 to 4 nodes per subject, with 150 subjects we expect to excise  $3.5 \times 150 = 525$  nodes. With 3.5 nodes per subject on average and an ICC at most 0.125 we will have VIF at most  $1 + (2 \times 3.5 - 1) \times 0.125 = 1.75$  and an ESS at least  $525 / 1.75 = 300$  nodes. Note that here  $m$  is twice the number of expected nodes per subject, since nodes will be identified using 2 different methods within the same subject. We expect the ICC to be at most 0.125 based on our estimate of the ICC = 0.07 from Crane et al..

With an ESS of at least 300 Ns we will have at least 82% power to reject  $H_{01}$  above and claim non-inferiority of PINPOINT with respect to Blue dye. This sample size calculation was

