performed using nQuery Advisor ® 7.0 (Copyright © 1995-2007, Statistical Solutions, Saugus, MA). We will test the hypothesis using a two-sided 95% confidence interval (i.e., two-sided significance level of 0.05). We will enroll subjects and identify Ns using both Blue dye and PINPOINT as described above in section 8.3.1.5 until we have at least 525 LNs identified, regardless of the method used to identify them. We expect that we will enroll approximately 150 subjects to obtain 525 nodes (based on clinical literature suggesting an average of 3-4 Ns excised per subject).

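### The primary endpoint's denominator is worded in two ways, and the wording that counts every excised node loosens the fixed 5-point margin to 5/c points, where c is the share confirmed as lymphoid

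*Protocol*

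**What the plan says.** Protocol 10.2 defines both numerators as nodes found by the method "and confirmed as lymphoid tissue, and we define the numerator for" the other method in the same terms. It sets one common denominator, nodes found by any method (classes 1 to 7), and adds: "The denominator will include excised nodes confirmed as lymphoid tissue". The following paragraph describes the same two proportions as confirmed nodes "divided by the total number of LNs identified and excised, across all subjects", with no histology condition on the divisor. The SAP, under Primary Efficacy Outcome, repeats both statements and does not choose between them.

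Elsewhere the protocol gives only the second form. The Primary Variables entry in the Summary has "divided by the total number of LNs identified and excised", and the effectiveness definitions in the Summary's study design and in 3.1 agree with it. The third secondary outcome (10.6 and the SAP) carries only the confirmed-node sentence.

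The margin is absolute: "A non-inferiority margin of 0.05 was determined to be clinically significant based on feedback from Investigators". Protocol 10.4 assumes detection rates "of 84% and 80% using ICG and Blue dye, respectively", bases the effective sample size (ESS) on nodes excised, and stops enrolment at 525 nodes identified. Neither count requires histological confirmation.

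**The concern.** The two denominators differ whenever an excised specimen proves not to be lymphoid. SAP Table 3 has a row for that result under every identification method, so the plan expects it to be possible.

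With all excised specimens in the denominator, each non-lymphoid one counts as a failure for PINPOINT and for Blue dye alike. It says nothing about which method is better, but it pulls the difference towards zero. The margin does not move with it, so tissue that is not a node makes non-inferiority slightly easier to claim. Two statisticians following the same SAP could also report different primary results, and c is known only once histology is in. In an open-label pivotal trial the denominator should not still be open at that stage.

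**Working it through.** **Inputs.** From protocol 10.2 and 10.4: margin 0.05; rates 0.84 and 0.80; "two-sided significance level of 0.05", which is 2.5% one-sided for non-inferiority; 525 nodes at 3.5 per subject; intra-cluster correlation 0.125. Assumed, because the documents do not give it: c = 0.95, 0.90 or 0.85.

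**The plan's own figure.** The variance inflation factor is 1 + (2 × 3.5 − 1) × 0.125 = 1.75, so ESS = 525/1.75 = 300. With unpooled variances, SE = √[(0.84 × 0.16 + 0.80 × 0.20)/300] = √(0.2944/300) = 0.0313. Power = Φ(0.09/0.0313 − 1.96) = 81.9%. This reproduces the statement "we will have at least 82% power to reject" the null hypothesis.

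**Effect on the margin.** Let N be nodes excised, L nodes confirmed, c = L/N, and x_t, x_c the two numerators. Then (x_t − x_c)/N = c × (x_t − x_c)/L. A margin of 0.05 on the N scale is therefore 0.05/c on the L scale.

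**Effect on one-sided error.** Take a true deficit of 5 points on confirmed nodes, 75% against 80%. Assume the methods are independent within a node. The discordant shares are 0.75 × 0.20 = 0.15 and 0.25 × 0.80 = 0.20, total 0.35. On the N scale with ESS 300:

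- difference = −0.05c
- SE = √{[0.35c − (0.05c)²]/300}
- P(lower limit > −0.05) = Φ[(0.05 − 0.05c)/SE − 1.96]

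| c | Margin on confirmed nodes (points) | Difference on N scale (points) | SE | One-sided error |
|---|---|---|---|---|
| 1.00 | 5.0 | −5.00 | 0.0340 | 2.5% |
| 0.95 | 5.3 | −4.75 | 0.0332 | 3.0% |
| 0.90 | 5.6 | −4.50 | 0.0323 | 3.6% |
| 0.85 | 5.9 | −4.25 | 0.0314 | 4.3% |

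A clustered simulation (150 subjects, 3 or 4 nodes each, intra-cluster correlation 0.07 and 0.125, 4,000 runs per setting) used a ratio-estimator variance in place of the cited Z₀ variance. With all excised nodes the error was 3.0–3.3% at c = 0.95 and 3.6–4.3% at c = 0.90. With confirmed nodes it stayed at 2.4–2.8%.

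**Can the choice change the result?** Illustration without clustering: 525 excised, 472 confirmed, 142 discordant, PINPOINT two nodes fewer.

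- All excised: difference −2/525 = −0.38 points, SE 2.27 points, lower limit −4.83. Non-inferior.
- Confirmed: difference −2/472 = −0.42 points, SE 2.52 points, lower limit −5.37. Not shown.

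**Power on the confirmed basis.** If 525 remains a count of excised or identified nodes and the inflation factor is held at 1.75, the confirmed ESS is 300c. At c = 0.95 it is 285, SE = √(0.2944/285) = 0.0321, power 80.0%. At c = 0.90 it is 270, SE = 0.0330, power 77.8%. If the inflation factor is recomputed for fewer nodes per subject, the loss is smaller. At c = 0.90 it becomes 1 + (6.3 − 1) × 0.125 = 1.6625, ESS = 472.5/1.6625 = 284 and power is about 80%. Keeping 525 confirmed nodes needs 525/c excised: 553 at c = 0.95, 584 at c = 0.90.

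**The case against.** The strongest reply is that an operative definition already exists. The formal sentences in 10.2 and the SAP point to confirmed nodes, the third secondary outcome has only that version, and the competing phrase is a looser restatement. Tissue that histology shows is not lymphoid is arguably not a lymph node, so the two wordings might be reconciled. Much of this stands: confirmed nodes is the better reading. It does not close the matter. The denominator sentence says what is included without saying that the rest is excluded. The restatement in 10.2 treats histological confirmation as a further condition on a node already called an LN. SAP Table 3, whose title refers to lymph nodes, has rows for specimens that are not lymphatic tissue. The formal primary-variable entry in the Summary carries only the wider wording.

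The reply on size also stands. Both interval limits scale by almost exactly c, so the decision changes only if the confirmed-node lower limit falls between −0.05/c and −0.05. That window is 0.3 to 0.9 points wide for c from 0.95 to 0.85. The plan expects PINPOINT to do better, and a result near 84% against 80% may well give the same verdict either way. Scaling does not change sign, so the superiority test is essentially unaffected.

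A reader might infer that the plan has adopted the looser denominator and will test at an inflated error rate. The documents do not support that: they leave the choice unsettled, lean towards confirmed nodes, and give no value of c. Nor does the 82% power figure show which denominator was meant. Multiplying the assumed rates by 0.90 in the unpaired formula gives 66.9%, but that ignores pairing. The paired calculation gives 82.5%.

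**Conclusion.** The point holds as an unresolved ambiguity in the primary endpoint, with the formal definition favouring confirmed nodes. If the wider wording were applied, the 5-point margin would become 5.3, 5.6 or 5.9 points on confirmed nodes, and one-sided error at a true 5-point deficit about 3.0%, 3.6% or 4.3% instead of 2.5%, for c = 0.95, 0.90 or 0.85. The margins depend only on the assumed c. The error rates also rest on ESS 300 and on independence of the methods within a node. At c = 1 there is no effect. The direction favours the test device and the size is modest. It should be corrected because it concerns the primary claim and can be settled before c is known.

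**What to change.** 1. Use one denominator in the Summary, 3.1, 10.2 and the SAP: excised nodes in classes 1 to 7 confirmed as lymphoid tissue. Remove the competing phrase in each place.
2. Report non-lymphoid specimens by method in SAP Table 3, which already has the rows, and give the all-excised version as a sensitivity analysis.
3. State whether a node with missing histology enters the common denominator in the best-case and worst-case analyses (10.2, 10.3, 10.7 and the SAP). Those rules make the same node lymphoid for one method and non-lymphoid for the other, so under a confirmed-only denominator its place is undefined.
4. Put the ESS and the 525-node count in 10.4 on confirmed nodes, or keep the counts and restate the power.

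The cost is more than aligning text. Keeping 525 as a count of identified nodes means a slightly less favourable stated power, about 80% at c = 0.95 and 78% at c = 0.90 by the plan's formula with its inflation factor of 1.75. Counting confirmed nodes means somewhat more excised nodes, hence more subjects. No new data are needed, since histology is already planned for every excised node.
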